### ***Sensitivity analyses***

Tipping point analysis based on the control-based MI method will be performed to examine the robustness of the results from the primary analysis (7). Patients who were randomized to SAR425899 dosing groups and liraglutide group and had no value at Week 26 will be given a penalty of 0.2%, ie, they are assumed to have received a treatment inferior to placebo by 0.2%. The penalty will be gradually increased by 0.2% at a time to evaluate at which level the conclusion of the analyses in terms of statistical significance is changed for the first trend test. The tipping point is the penalty level, at which the magnitude of efficacy reduction in patients without HbA1c value at Week 26 creates a shift in the treatment effect of each of SAR425899 dose group so that the trend test result becomes insignificant. The steps to perform the tipping point analysis are as follows:

1. Missing data will be imputed using control-based MI (see sample code Part 1b in [Appendix D](#)),
2. All imputed Week 26 HbA1c values in the SAR425899 dose groups and Liraglutide group will be penalized by adding 0.2% in each complete dataset (see sample code Part 1b in [Appendix D](#)),
3. Change from baseline at Week 26 in HbA1c will be analyzed using the same ANCOVA model as specified in the primary analysis in each complete dataset (see sample code Part 2 in [Appendix D](#)),
4. Results will be combined across complete datasets using Rubin's rule (see sample code Part 3 in [Appendix D](#)),
5. Steps 2 to 5 will be repeated with penalty increased by 0.2% until the p-value for the first trend test is >0.05.

## Summary statistics at scheduled visits

Summary statistics (for screening value, baseline value, observed values, and observed changes from baseline) at scheduled visits (using OC) will be provided for each treatment group. The summary will include the number of observations, mean, SD, standard error (SE), minimum, median, and maximum. Graphical presentations will also be used to examine trends over time using mean values ( $\pm$ SE) and mean changes from baseline ( $\pm$ SE) at each of the scheduled visits. These analyses will be performed using efficacy assessments obtained during the 26-week treatment period, including those obtained after IMP discontinuation or introduction of rescue therapy.

### 2.4.4.2 Analyses of secondary efficacy endpoints

Descriptive statistics (number, mean, standard deviation, median, minimum, and maximum) will be provided by treatment for all continuous secondary variables at the scheduled visits.

All continuous secondary efficacy endpoints at Week 26 defined in [Section 2.1.3.2](#) will be analyzed using the same ANCOVA model with missing post baseline values imputed by placebo control-based MI method as described in [Section 2.4.4.1](#) to compare each SAR425899 dose group with placebo. For missing value at baseline, missing data will be imputed using the same MI under the MAR assumption as described in [Section 2.4.4.1](#). The model will include fixed effect terms of treatment groups (SAR425899 0.12 mg, SAR425899 0.16 mg, SAR425899 0.20 mg, placebo and liraglutide), randomization strata of screening HbA1c value ( $<8$ ,  $\geq 8\%$ ), randomization strata of Visit 4 (Day 1) BMI ( $<35.0$  kg/m^2,  $\geq 35.0$  kg/m^2), and country, and the covariate of baseline value. The three trend tests described in [Section 2.4.4.1](#) are planned on body weight only. For all continuous secondary efficacy endpoints, means and adjusted means of each treatment group will be provided, as well as adjusted mean and associated two-sided 95% CI of the differences between each SAR425899 dose group and placebo. The analyses include values at baseline and Week 26 (observed or imputed) regardless of treatment discontinuation or initiation of rescue therapy.

All categorical secondary efficacy endpoints defined in [Section 2.1.3.2](#) will be analyzed using a Cochran-Mantel-Haenszel (CMH) method stratified on randomization strata of screening HbA1c value ( $<8$ ,  $\geq 8\%$ ) and randomization strata of Visit 4 (Day 1) BMI ( $<35.0$  kg/m^2,  $\geq 35.0$  kg/m^2). The proportion in each treatment group will be provided, as well as the difference of proportions between each SAR425899 dose group and placebo with associated 2-sided 95% CI. For HbA1c ( $<6.5\%$ ,  $<7\%$  respectively at Week 26) and body weight ( $\geq 5\%$ ,  $\geq 10\%$  body weight loss respectively from baseline at Week 26) responders, all values at Week 26 will be used to determine whether a patient is a responder or not, even if they are measured after IMP discontinuation or rescue medication use. Patients who have no measurement at Week 26 will be treated as non-responders.

[figure not shown]
For percentage of patients requiring rescue therapy, patients who have received rescue therapy during the 26-week treatment period will be summarized.

For HbA1c and body weight responders, a sensitivity analysis will be performed treating patients as non-responders if they receive rescue therapy, or have no measurement at Week 26. The sensitivity analysis includes measurement at Week 26, regardless of treatment discontinuation.

### 2.4.4.3 Multiplicity issues

To control the type I error, a hierarchical testing procedure will be applied. The testing procedure will be performed to test the primary and secondary efficacy variables (HbA1c and body weight) by the following prioritized order. The test stop as soon as an endpoint is found not statistically significant at  $\alpha=0.05$  (2-sided).

Figure 1 - The hierarchical testing procedure

No multiplicity adjustment will be made on other secondary efficacy variables other than body weight.

## 2.4.5 Analyses of safety data

The summary of safety results will be presented by treatment group.

The “observation period” defined in [Section 2.1.4](#) is applicable in all safety analyses for the classification of AEs, potentially clinically significant abnormality (PCSA) values for the laboratory, vital sign, ECG and Holter monitoring.

### *General common rules*

All safety analyses will be performed on the safety population as defined in [Section 2.3.2](#), unless otherwise specified, using the following common rules:

- Safety data in patients who do not belong to the safety population (eg, exposed but not randomized) will be listed separately;
- The baseline value is defined as the last available value before the first injection of IMP.
- The PCSA values are defined as abnormal values considered medically important by the Sponsor according to predefined criteria/thresholds based on literature review and defined by the Sponsor for clinical laboratory tests, vital signs, and ECG (PCSA version dated May 2014 [[Appendix A](#)]).
- PCSA criteria will determine which patients had at least 1 PCSA during the TEAE period, taking into account all evaluations performed during the TEAE period, including unscheduled or repeated evaluations. The number of all such patients will be the numerator for the treatment-emergent PCSA percentage;
- The treatment-emergent PCSA denominator by group for a given parameter will be based on the number of patients assessed for that given parameter during the TEAE period by treatment group in the safety population;
- For laboratory parameters cited in the protocol as efficacy endpoints (including HbA1c and plasma glucose), PCSA summaries will not be provided. These parameters will be summarized in [Section 2.4.4](#);
- For quantitative safety parameters based on central laboratory/reading measurements, descriptive statistics will be used to summarize results and change from baseline values by visit and treatment group. Summaries will include the last on-treatment value (see [Section 2.4.5.4](#));
- The analysis of the safety variables will be essentially descriptive and no systematic testing is planned. Relative risks versus placebo and their 95% CIs may be provided, if relevant;
- Selected safety analyses will be summarized by age group (<50, ≥50 to <65, ≥65 to <75, ≥75 years of age), gender, race subgroups, and any pertinent subgroups as appropriate (see details in [Section 2.4.5.1](#) and [Section 2.4.5.2](#)).

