9.2 SECONDARY ENDPOINTS

9.2.1 Secondary efficacy endpoints

- Change in body weight from baseline to Week 26.
- Percentage of patients achieving predefined HbA1c targets of <7% and <6.5% at Week 26.
- Percentage of patients achieving $\geq 5\%$ and $\geq 10\%$ body weight loss at Week 26.
- Change in FPG from baseline to Week 26.
- Change in 7-point SMPG profile from baseline to Week 26 (each time point and mean daily value).
- Change in PPG in response to a standardized meal test in up to 50% subset of all patients from baseline to Week 26 at time points premeal, 10mn, 20mn, 0.5h, 1h, 1.5h, 2h, 3h, 4h post meal, and associated glucose excursion values at these time points.
- Percentage of patients requiring rescue therapy during 26-week treatment period.
- Change in fasting insulin, pro-insulin, and C-peptide from baseline to Week 26, change in postprandial insulin, proinsulin and C-peptide in response to a standardized meal test in up to 50% subset of all patients from baseline to Week 26 at time points premeal, 10mn, 20mn, 0.5h, 1h, 1.5h, 2h, 3h, 4h post meal, and associated excursion values for each of the above parameters at these time points

- Change in β -cell function assessed by HOMA- β from baseline to Week 26.
- Change in insulin resistance assessed by HOMA-IR from baseline to Week 26.
- Change in fasting lipid profile (total cholesterol, triglycerides, LDL-C, and HDL-C), free fatty acids, and ketone bodies from baseline to Week 26.
- Changes in PD biomarkers assessments from baseline to Week 26 will be performed on the following variables:
 - Waist circumference, hip circumference, waist to hip ratio,
 - VAS for appetite/satiety score,
 - Fasting levels of adiponectin.

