11.4.3 Analyses of safety data

The summary of safety results will be presented by treatment group.

All safety analyses will be performed on the safety population as defined in [Section 11.3.2](#) using the following common rules:

The baseline value is defined as the last available value prior to the first injection of IMP.

The following definitions will be applied to laboratory parameters, vital signs and ECG.

- The potentially clinically significant abnormality (PCSA) values for clinical laboratory tests, vital signs and ECG are defined as abnormal values considered medically important by the Sponsor's Global Pharmacovigilance and Epidemiology department and in effect at the time of the final statistical analysis plan approval. Potentially clinically significant abnormality criteria for parameters not cited in the protocol as safety parameters will not be analyzed.
- Potentially clinically significant abnormality criteria will determine which patients had at least 1 PCSA during the on-treatment period, taking into account all evaluations performed during the on-treatment period, including unscheduled or repeated evaluations. The number of all such patients will be the numerator for the on-treatment PCSA percentage.

The "observation period" defined in [Section 9.2.2](#) are applicable for classification of AEs, determination of on-treatment PCSA values and the last on-treatment value for the laboratory, vital sign and ECG parameters.

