**Table 1 - Protocol amendment statistical changes**

Amendment Number	Date Approved	Rationale	Description of statistical changes
1	23-Jan-2017	
Increased urinary free-cortisol level was observed in animal studies of SAR425899 but the relevance of this finding to human is unclear. The Food and Drug Administration (FDA) requested to add the measurement of urinary free-cortisol and creatinine from 24h urines at baseline and end of treatment in order to assess the increase in urinary free-cortisol in humans which may suggest a potential effect of SAR425899 on the hypothalamic-pituitaryadrenal axis.
 
In phase I studies an increase of ketones bodies was observed for the SAR425899 high dose group (up to 0.18 mg) but not for placebo and the SAR425899 low dose group. In view of the currently requested administration of up to 0.20 mg of SAR425899 and the potential gastrointestinal side effects together with the simultaneous administration of metformin, the BfArM recommended to consider metabolic acidosis as an adverse event of special interest with an immediate notification in order to recognize this state very early in the study and to discontinue the administration of metformin when applicable.
 
Leptin and microRNA were initially considered as biomarkers of interest in this study. Leptin plasma concentrations are correlated with fat mass. MicroRNA is a surrogate biomarker for nonalcoholic steatohepatitis (NASH). Thus assessment of these two biomarkers was expected to provide information about SAR425899 effect on fat mass and NASH. However the sponsor decided to not measure these parameters anymore during this phase II study. For Leptin, it is not required for any modeling and is not recommended as a surrogate to test for differences in energy expenditure. Nevertheless Leptin and fat mass changes are planned to be assessed in a study dedicated to energy expenditure assessment. For MicroRNA, patients included in this study are not diagnosed for NASH and no liver biopsy is taken which could make the interpretation of microRNA results difficult. Nevertheless microRNA is planned to be assessed in a study dedicated to NASH.
	
To add urinary free-cortisol and creatinine measured in 24 hours urines at baseline and in Visit 12 (Week 26, End of treatment).
 
To add metabolic acidosis as a new adverse event of special interest as requested by the BfArM.
 
To remove Leptin and microRNA assessments

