### **2.1.3.2 Secondary efficacy endpoint(s)**

#### **Continuous secondary efficacy endpoints**

The continuous secondary efficacy endpoints are:

- Change in body weight from baseline to Week 26,
- Change in FPG from baseline to Week 26,
- Change in 7-point SMPG profiles from baseline to Week 26 (each time point and average daily value),
- Change in PPG and in blood glucose excursion in response to a standardized meal test in up to 50% subset of all patients from baseline to Week 26 at time points premeal, 10 min, 20 min, 0.5 h, 1 h, 1.5 h, 2 h, 3 h, 4 h post meal,
- Change in fasting insulin, proinsulin, and C-peptide from baseline to Week 26,
- Change in insulin, proinsulin, and C-peptide and associated excursion values in response to a standardized meal test in up to 50% subset of all patients from baseline to Week 26 at time points premeal, 10 min, 20 min, 0.5 h, 1 h, 1.5 h, 2 h, 3 h, 4 h post meal,
- Change in HOMA- $\beta$  and HOMA-IR from baseline to Week 26,
- Change in lipid profile (total cholesterol, triglycerides, LDL-C, and HDL-C) and free fatty acids, and Ketone bodies from baseline to Week 26,

For 7-point SMPG profiles, the mean daily (ie, average on 7 points) change from baseline to Week 26 will be analyzed. In addition, the change from baseline to Week 26 for each of the 7 points will be evaluated, respectively.

For FPG, only values assessed in fasting condition will be analyzed.

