#### **2.1.4.4 Laboratory safety variables**

Clinical laboratory data consists of blood analysis (including hematology and clinical chemistry, amylase, lipase, calcitonin) and urinalysis (albumin/creatinine ratio). Clinical laboratory values will be summarized in both standard international units and conventional units.

The laboratory data will be collected at designated visits (see study flowchart in [Appendix C](#). The following laboratory data will be measured at a central laboratory and used as safety endpoints:

- Hematology
  - Red blood cells, platelets: hemoglobin, hematocrit, red blood cells (erythrocytes) count, platelets count.
  - White blood cells: white blood cells count, and differential counts (neutrophils, lymphocytes, monocytes, basophils, and eosinophils).
- Clinical chemistry
  - Electrolytes: sodium, potassium, calcium, phosphorus.
  - Renal function: creatinine, calculated eGFR, cystatin C, uric acid.
  - Liver function: alanine aminotransferases (ALT), aspartate aminotransferases (AST), alkaline phosphatase (ALP), gamma-glutamyl transpeptidase (GGT), total bilirubin (and, in case of values above the normal range, differentiation in conjugated and non-conjugated bilirubin).
- Thyroid panel: Thyroid-stimulating hormone (TSH), Total Triiodothyronine (T3) and Free Thyroxine (FT4).
- Pancreatic enzymes: lipase, amylase.
- Serum calcitonin.
- Urine analysis: albumin/creatinine ratio.
- Urinary free-cortisol and creatinine based on 24-hour urine sample in some patients, 24-hr free-cortisol/creatinine ratio will be derived for these patients.

Lipid parameters (fasting): total cholesterol, triglycerides, LDL-C, and HDL-C are presented as efficacy parameters in [Section 2.1.3.2](#).

Other laboratory data not mentioned above (serology tests (hepatitis B antigen, hepatitis C antibodies), serum pregnancy test, serum follicle-stimulating hormone [FSH], and estradiol) will not be defined as safety endpoints (collected as per study flowchart in [Appendix C](#)).

Technical formulas are described in [Section 2.5.1](#).

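### Ketone bodies, part of the reason for the metabolic acidosis AESI, are analysed only as an efficacy endpoint, so no planned output counts patients with on-treatment elevations

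*SAP*

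**What the plan says.** **Signal.** The amendment history in SAP 1.5, Table 1, records: "In phase I studies an increase of ketones bodies was observed for the SAR425899 high dose group (up to 0.18 mg"). The rise was not seen on placebo or at low dose. The same entry cites the 0.20 mg dose, potential gastrointestinal effects and simultaneous metformin, and the resulting change was "To add metabolic acidosis as a new adverse event of special interest as requested by the BfArM".

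**Classification.** Protocol 9.2.1 lists among the secondary efficacy endpoints "Change in fasting lipid profile (total cholesterol, triglycerides, LDL-C, and HDL-C), free fatty acids, and ketone bodies from baseline to Week 26". SAP 2.1.3.2 does the same ("and free fatty acids, and Ketone bodies from baseline to Week 26").

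**Safety lists.** Neither Protocol 9.2.2.4 nor SAP 2.1.4.4 names ketone bodies. For urine, the SAP list has "Urine analysis: albumin/creatinine ratio" plus 24-hour free cortisol and creatinine. The flow chart's central-laboratory urinalysis includes ketones, at screening, baseline, Week 14 and Week 26.

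**Exclusions.** SAP 2.4.5, General common rules: "For laboratory parameters cited in the protocol as efficacy endpoints (including HbA1c and plasma glucose), PCSA summaries will not be provided". Protocol 11.4.3: "Potentially clinically significant abnormality criteria for parameters not cited in the protocol as safety parameters will not be analyzed". (PCSA: potentially clinically significant abnormality.)

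**What is planned.** SAP 2.4.4.2 gives continuous secondary endpoints by-visit descriptive statistics and a Week 26 ANCOVA on the ITT population. Missing post-baseline values in the active arms are imputed as if the patient had been on placebo throughout (SAP 2.4.4.1). Metabolic acidosis is counted as an AESI category (SAP 2.4.5.2).

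**The concern.** The sponsor's own amendment treats a ketone rise as a possible harm that deserves early recognition, yet every analysis of the measurement sits in the efficacy section. Safety laboratory variables get a count of patients with abnormal values, by baseline status and treatment group, plus a listing. Ketone bodies get neither. The one between-group comparison uses an imputation chosen to be conservative for benefit. For a harm it works the other way, because it moves the active arms towards placebo.

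At stake is whether the study report can say how many patients at each dose had raised ketones while on drug. A dose-finding trial that goes above the phase 1 exposure should be able to answer that.

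**Working it through.** The documents state no figure for ketone bodies, so there is none to reproduce. The check is first textual, then a bounded illustration.

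**Step 1. Which planned output would count patients with an on-treatment elevation?**

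| Output | Data | Counts them by group? |
|---|---|---|
| PCSA summary (SAP 2.4.5, 2.4.5.4) | Safety population, TEAE period | No: efficacy parameters are excluded |
| Normal-range table and abnormal-value listing (SAP 2.4.5.4) | Safety population, TEAE period | No: scope is the 2.1.4.4 list |
| By-visit statistics (SAP 2.4.4.2, 2.5.4) | ITT as randomized, observed values | No: N, mean, SD, median, minimum, maximum |
| Week 26 ANCOVA (SAP 2.4.4.2) | ITT, observed or imputed | No: adjusted mean difference |
| AESI counts (SAP 2.4.5.2) | Reported events | No: metabolic acidosis only |

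Adverse event tables do not close the gap. Under Protocol 10.4.3 a laboratory abnormality becomes an adverse event only if it is symptomatic, needs treatment or consultation, leads to a dosing change or discontinuation, is serious, or is itself an AESI. Raised ketones are not on the AESI list, so an asymptomatic rise need not be recorded as an event.

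**Step 2. Population.** The by-visit statistics include values taken after IMP has stopped. Protocol 9.2.2.1 equates 3 days with about 5 half-lives, so later values are effectively off drug. They are also grouped as randomized, although dose reduction is allowed before Week 8 and SAP 2.3.2 groups safety data by the dose received from Week 8.

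**Step 3. A parallel case.** The same amendment added urinary free cortisol after an animal finding, and SAP 2.1.4.4 lists it as a safety variable. Ketone bodies, with a human finding, were not added.

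**Step 4. Visits.** Ketone bodies are sampled at baseline and at Weeks 4, 8, 14, 20 and 26. Of 5 post-baseline visits, 1 enters the ANCOVA and 4 are descriptive only.

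**Step 5. Pull of the imputation (assumed inputs).** Let d be the fraction of an active arm with no Week 26 value, and ρ the correlation of the last observed with the Week 26 value. Take the same treatment shift at both times and missingness unrelated to level. If the imputation uses the earlier value, the share of the true difference retained is (1 − d) + dρ, so the loss is d(1 − ρ).

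| d | ρ = 0 | ρ = 0.3 | ρ = 0.5 | ρ = 0.7 |
|---|---|---|---|---|
| 10% | 0.90 | 0.93 | 0.95 | 0.97 |
| 20% | 0.80 | 0.86 | 0.90 | 0.94 |
| 30% | 0.70 | 0.79 | 0.85 | 0.91 |

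A simulation of this imputation agreed to within about 0.01. The loss runs from 0.10 × 0.3 = 3% to 0.30 × 1 = 30%.

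**Step 6. Means against counts (assumed inputs).** Suppose 3 of 60 patients in one dose arm rise by 3 SD. The arm mean moves 3 × 3/60 = 0.15 SD. The 95% CI half-width for 60 versus 30 is 1.96 × √(1/60 + 1/30) = 0.44 SD. The mean comparison can miss this even with complete data. A count table would show 3/60 = 5%, if a rise of that size is out of range.

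**The case against.** The strongest reply is that ketone bodies are neither hidden nor unmonitored, and most of it stands.

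- **Observed values are reported.** By-visit statistics, maximum included, cover every ketone visit and are untouched by imputation. Ketone bodies are also measured at a premature discontinuation visit, and SAP 2.5.4 allocates that value to a scheduled visit, normally when no scheduled value already fills it.
- **Stopping drug is not leaving the study.** Patients who discontinue IMP are to be followed to the planned end, and their observed Week 26 values are used. Imputation affects only those with no Week 26 value.
- **No safety laboratory variable gets a formal test.** The safety analysis is descriptive, so the lack of between-group comparisons at Weeks 4 to 20 is not a defect peculiar to ketones.
- **The clinical event is covered.** Metabolic acidosis is reported within 24 hours, counted and listed. An independent DMC reviews unblinded safety data under its own SAP.
- **The efficacy placement has a rationale.** Protocol 9.5 cites glucagon's effects on lipid metabolism and lipolysis.
- **Other tables are possible.** Protocol 11.4.3.3 permits shift tables for laboratory tests of interest, but only as an option. SAP Appendices A and B were not in the text available. Even if Appendix A holds a ketone criterion, the rule in 2.4.5 switches its summary off.

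A reader might infer three stronger things that the documents do not support. One is that patients with an early rise contribute nothing to the Week 26 comparison. That would need all of them to leave the study and an imputation that ignores earlier visits; no dropout rate is given, and the code in SAP Appendix D could not be checked. Another is that the ketone finding alone produced the AESI, whereas Table 1 gives it alongside dose, gastrointestinal effects and metformin. The third is that patients eating poorly have the highest ketones and stop early, for which the documents offer no source.

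None of this supplies the missing item, which is a patient count by dose.

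**Conclusion.** The point holds as a gap in safety reporting. Both documents route ketone bodies to efficacy only, and the stated exclusions then remove the abnormal-value table and listing that a safety laboratory variable would receive. This follows from the text and needs no assumption beyond Appendix B not listing a separate ketone table.

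The size of the imputation effect is conditional: a partial pull towards zero of 3% to 30% over the assumed ranges for missingness and correlation. It would be larger if missing values were concentrated in patients with high ketones, which the documents neither state nor exclude. It concerns the Week 26 ANCOVA alone. The primary endpoint is unaffected. The change should be made because it is cheap and recovers information that the present rule suppresses.

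**What to change.** - Add ketone bodies, and the urine ketone result already collected, to SAP 2.1.4.4.
- Exempt them from the efficacy-parameter exclusion in SAP 2.4.5, and note the departure from the corresponding sentence in Protocol 11.4.3.
- On the safety population in the TEAE period, tabulate the number (%) of patients above the laboratory normal range by baseline status and treatment group, with a listing, in the format SAP 2.4.5.4 already uses where no PCSA criterion exists. For urine ketones, use the laboratory's reported categories. The on-treatment maximum is an optional addition; it is not planned for other laboratory variables.
- Keep the Week 26 efficacy ANCOVA, and state that its control-based imputation is not to be read as evidence on safety.

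The cost is SAP wording and one or two extra tables from data already collected, with no new sampling and no change to the efficacy analyses.
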